## What is already known on this subject?

## What does this study add?

Acute respiratory distress is medical emergency in children and infants, approximately 15- 20% of affected children require respiratory support and intensive care due to a rapid emergency of respiratory distress, it's a major cause of death in children under 5 years.

The study will discuss which is better Nasal Continuous Positive Airway Pressure or High Velocity Nasal Insufflation in treatment of children with acute respiratory distress that require oxygen therapy in PICU.

## 1. Introduction/ Review

Acute respiratory distress is medical emergency in children and infants (**Friedman and Nitu, 2018**).

Approximately 15–20% of affected children require respiratory support and intensive care due to respiratory distress (**Meissner et al., 2016**).

Acute Respiratory distress is a major cause of death in children under 5 years and approximately one million children die annually due to respiratory failure worldwide (**Walker et al., 2013**).

The World Health Organization and the American Academy of Pediatrics (AAP) both recommend oxygen supplementation at an arterial pulse oximetry (SpO2) lower than 90% because oxygen supply in children with acute lower respiratory tract infection is associated with reduced mortality (**Duke et al., 2008**).

Different modalities for oxygen supplementation in children exist, the standard flow oxygen therapy (through a standard nasal cannula) provides oxygen without need for humidification when the oxygen flow is either low (i.e., 1–2 L/min) or the room air has high humidity (**Ralston et al., 2014**).

On the other hand, high flow rates usually require humidification due to the drying effect of non-humidified cold oxygen on nasal secretions and the respiratory mucosa (**Franklin et al., 2018**).

Non-invasive ventilation is widely used in the respiratory management of severe cases of respiratory distress, high-flow nasal cannula (HFNC) oxygen therapy delivers warm and humidified oxygen at a higher flow than the normal inspiratory flow (**Lee et al., 2013**).

The nasal continuous positive airway pressure is another management modality that combines supplemental oxygen with a positive end-expiratory pressure, it has been shown to reduce the ventilation need duration and the overall hospitalization length in children with respiratory distress (**Essouri et al., 2014**).

Both CPAP and High Velocity Nasal Insufflation are high flow systems and are

capable of generating PEEP (*Pedersen and Vahlkvist, 2017*).

High Velocity Nasal Insufflation is considered to be a less invasive procedure than CPAP, better tolerated and comparatively easy to perform (*Yoder et al., 2013*).

This probably makes High Velocity Nasal Insufflation a preferred procedure of choice in young children. One of the important differences between these two procedures is that CPAP employs an integrated pressure release valvular system, whereas in High Velocity Nasal Insufflation, the release of pressure is via the leak at the nares prong interface and through the mouth (*Pedersen and Vahlkvist, 2017*).

The lack of the ability to regulate the pressure delivered to the airways in High Velocity Nasal Insufflation may run the risk of delivering high pressures at high flow rates if the leak is compromised (*Sivieri et al., 2013*).

High Velocity Nasal Insufflation is thought to work through increasing the oxygen fraction in the alveoli by washout of the nasopharyngeal dead space, reducing the inspiratory resistance, improvement of airway conductance and by providing an end-distending pressure to the lungs (*Dysart et al., 2019*).

On similar lines, CPAP decreases the inspiratory resistance, reduces atelectasis, reduces alveolar resistance, increases surface area of alveoli, and enhances ventilation and perfusion (V/Q) matching through PEEP (*Gupta and Donn, 2016*).

A retrospective record-based study to compare CPAP with High Velocity Nasal Insufflation among infants with respiratory distress found no significant difference in length of hospital stay, respiratory rate, PaCO2, FiO2, or duration of oxygen supply (*Metge et al., 2014*).

## 2. Aim/Objectives

To study outcome & tolerability of High Velocity Nasal Insufflation and Continuous Positive Air way Pressure in children with acute respiratory distress assessed by chest ultrasound in PICU.

## 3. Methodology:

### Patients and Methods/ Subjects and Methods/ Material and Methods

- **Type of Study Design:** Cohort Study Design.
- **Proposed Study Design:** Prospective Interventional Study.
- **Study setting:** PICU, Children's Hospital, Faculty of Medicine, Ain Shams University, Cairo, Egypt.
- **Study duration:** Two years starting from December 2022 to December 2024.
- **Study population:** Children aged 1 month - 5 years.
- **Sampling method:** Randomized sample.

– **Sample size:** 80 patients will be divided into 2 groups.

Group A: Patients on high velocity nasal insufflation .

Group B: Patients on nasal continuous positive airway pressure.

### **Inclusion criteria (for groups A and B)**

- Patients aged from 1 month to 5 years, hospitalized in PICU with acute respiratory distress failed on low flow nasal oxygen and need non invasive respiratory support .

**Exclusion criteria:** Any chronic diseases & comorbidites including

- Cardiac diseases.
- Neuromuscular diseases.
- Chronic lung diseases.
- Recurrent wheezing.
- History of cardio-respiratory arrest.

### **– Study procedures:**

The patients will be divided into two groups A and B, randomization will be done as follow: group A contains the patients with odd numbers and group B contains patients with even numbers and both groups will undergo the following:

**1-** Detailed medical history through patients and/or their legal guardian as well as data retrieved from patients' medical files compiled during admission and used for patient follow up post discharge, with emphasis on:

- a- Demographic data: age, gender, age at disease onset and consanguinity.
- b- History of the present illness with emphasis on systems affected in chronological order, with focus on respiratory affection e.g. Fever, cough, Shortness of breath, cyanosis.

**2-** General physical examination and respiratory examination for any residual findings at the time of the study, and retrieving data of examination findings from the medical files.

**3-** Results of Laboratory tests done for patients during and after hospital admission including CBC, blood gases, inflammatory markers including CRP, ESR, blood cultures and sputum cultures and viral respiratory panel.

**4-** Imaging results: chest ultrasound at day 0 then daily assessment by lung ultrasound score. Appendix 1

**5-** Assessment of pain by flacc pain rating scale. Appendix 2

– **Ethical Considerations:** This study will be conducted after approval of the Research Ethics Committee of Ain Shams University hospitals and an informed consent will be obtained from the parents or caregiver of each participant.

- **Statistical analysis:** Numerical data will be summarized using mean and standard deviations or medians and inter quartile ranges. Qualitative data will be presented as count and percentage, p-value <0.005 will be considered significant.
- **Statistical package:** Statistical analysis will be performed with statistical package for social science (SPSS) version 27.

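### Allocation by odd or even patient number is called randomization, but the arm can be known before a child is enrolled, so the comparison is open to selection bias

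*Protocol*

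**What the plan says.** Section 3 (Methodology) lists the sampling method as "Randomized sample" and also labels the study "Cohort Study Design". On size it says that "80 patients will be divided into 2 groups": group A receives high velocity nasal insufflation (HVNI) and group B nasal CPAP. The allocation method appears once, under Study procedures: "randomization will be done as follow: group A contains the patients with odd numbers and group B contains patients with even numbers".

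The protocol does not say what the number is, who gives it or when. It describes no random sequence, no concealment and no person independent of enrolment.

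Three other places bear on the point:
- The inclusion criteria admit children who "failed on low flow nasal oxygen and need non invasive respiratory support", with no threshold for failure or need.
- The Introduction says of HVNI: "This probably makes High Velocity Nasal Insufflation a preferred procedure of choice in young children".
- The stated purpose is comparative: "The study will discuss which is better Nasal Continuous Positive Airway Pressure or High Velocity Nasal Insufflation".

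**The concern.** Randomization protects a comparison in two ways. Chance alone decides the arm, and nobody deciding on entry knows the arm beforehand. The odd/even rule secures neither. Someone who knows that the next child will receive a given device can enrol, wait or pass over a child, and an entry criterion based on judgement leaves room to do so without breaking the protocol.

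The groups could then differ in severity at entry for reasons other than chance. A p-value cannot separate such a difference from a device effect. Since the study sets out to say which device is better, its central comparison is exposed, and the word randomized promises readers a protection that the method does not give. An analysis plan cannot repair this, because allocation is fixed in the protocol.

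**Working it through.** **1. Reading the rule.** The protocol leaves the number undefined, so each natural reading is taken in turn.

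| What the number is | When the arm is knowable | How foreknowledge could act |
|---|---|---|
| Order of enrolment | As soon as the previous child is allocated, even if the number is given after consent | Choosing which child takes the next slot, or waiting |
| File or admission number | Before eligibility is judged or parents are approached | Skipping or delaying a particular child |
| A randomly drawn, concealed number | Not in advance | None, but the text mentions no such source |

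Only the third reading would be sound, and nothing in the protocol supports it.

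**2. Predictability.** Applied to numbers 1 to 80, the rule gives 40 and 40, and anyone who knows it can name 80 of 80 assignments (100%). Under simple randomization the figure is 50%. For permuted blocks of randomly varying size 4, 6 or 8 (assumed sizes), a guesser who tracks every past allocation and always names the arm with fewer children so far is right 67.9% of the time by simulation.

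**3. Illustration of bias.** The protocol gives no figure from which bias could be computed, so these inputs are assumptions: enrolment-order numbering, 40 per arm, no true effect, a two-sample t-test, and two eligible children to choose from at each steered slot, the milder going to HVNI and the sicker to CPAP. The 0.005 level is the protocol's own (Statistical analysis).

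- The expected larger of two independent standard normal values is 1/√π = 0.564. Steering a share *s* of slots in both arms therefore gives a severity gap of 2 × 0.564 × *s* = 1.128*s* SD.
- If severity correlates *r* with outcome, the spurious outcome difference is *r* × 1.128*s* SD. For example, at *s* = 0.30 and *r* = 0.6 it is 0.6 × 0.338 = 0.20 SD.

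False-positive rates are from 100,000 simulated trials per scenario:

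| Slots steered | Severity gap (SD) | Spurious difference, *r* = 0.3 (SD) | False positives, *r* = 0.3 | Spurious difference, *r* = 0.6 (SD) | False positives, *r* = 0.6 |
|---|---|---|---|---|---|
| 0% | 0 | 0 | 0.48% | 0 | 0.50% |
| 10% | 0.11 | 0.03 | 0.53% | 0.07 | 0.71% |
| 20% | 0.23 | 0.07 | 0.71% | 0.14 | 1.42% |
| 30% | 0.34 | 0.10 | 1.01% | 0.20 | 2.84% |
| 50% | 0.56 | 0.17 | 1.97% | 0.34 | 9.62% |

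If only HVNI slots are steered, the differences halve. False positives for 20% to 50% steering are then 0.56% to 0.83% (*r* = 0.3) and 0.64% to 2.00% (*r* = 0.6).

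**4. Cross-check by formula.** Suppose enrolment shifts expected outcome by ±η SD according to the arm expected next, and a share *c* of guesses is correct. The bias is then 2η(2*c* − 1) SD. With 40 per arm the standard error is √(2/40) = 0.224 SD. Take η = 0.10:

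- Odd/even rule, *c* = 1: bias 0.20 SD. False positives are 2.8% at the 0.005 level, agreeing with the simulation at the same difference, and 14.6% at a 0.05 level.
- Random blocks, *c* = 0.679: bias 2 × 0.10 × 0.358 = 0.072 SD. False positives are 0.73% and 6.2%.
- Concealed simple randomization, *c* = 0.5: bias 0, and both rates stay nominal.

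**The case against.** Nobody can point to actual steering, and several details limit what the numbers show.

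- **Meaning of the number.** If it is a file number, its parity may be unrelated to severity, and the next arm cannot be read from the last child. That stands, but the arm is still knowable before the child is approached, so the exposure to selection remains.
- **Scope of the illustration.** Choosing between two children for a slot fits only the enrolment-order reading, and the 40/40 split needs consecutive numbers. That stands. The figures do not describe the file-number reading.
- **Plausibility of heavy steering.** Eighty children in two years is about one every 9 days (730/80 = 9.1), and the number of eligible children is not given. Two eligible children at half of all slots is a strong assumption. That stands, and the 50% row should carry no weight in judging severity.
- **Direction.** The Introduction leans towards HVNI, but also warns that delivered pressure cannot be regulated with it and cites a retrospective study that found no significant difference. A preference for HVNI could also send sicker children there. That stands: the direction is unknown, and reversing it changes the sign of the bias, not its size.
- **The sampling label.** The entry calling the sample randomized sits under sampling method and is weaker evidence than the allocation sentence. That stands, but the allocation sentence is enough by itself.

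None of these points supplies a random sequence or concealment.

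**Conclusion.** The concern holds. The protocol calls a deterministic, unconcealed rule randomization, and on either natural reading of the number the arm can be known before enrolment. The conclusion rests on the allocation sentence and on the absence of any random sequence or concealment elsewhere, not on the simulation. It claims an opening for selection bias, not that bias has occurred.

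The size of the bias cannot be derived from the document. The illustrated range runs from almost nothing at 10% steering to a few times the nominal false-positive rate at 20% to 30%. It depends on the assumed steering share, correlation, two-child choice, test and enrolment-order numbering. This must be fixed because allocation underpins the study's only comparison and analysis cannot reliably repair it.

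**What to change.** **If enrolment has not started or is still open.** In Study procedures, replace the odd/even rule with a computer-generated 1:1 sequence in randomly varying block sizes. A staff member who does not enrol children prepares it in sequentially numbered, sealed, opaque envelopes or an equivalent, each opened only after eligibility and consent are recorded. If some children were already allocated by number, state how many and report them separately from those allocated by the concealed list.

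**If all children were allocated by the rule.** The study window in Section 3 closes in December 2024, so this may apply.
- Remove the word randomized from the sampling and allocation text, and call the study quasi-randomized.
- State what the number was and when it was given.
- Report baseline severity by arm, including the day 0 lung ultrasound score already planned ("chest ultrasound at day 0 then daily assessment by lung ultrasound score").
- Where records allow, report eligible children who were not enrolled, by the arm that their number would have given.
- Temper causal claims.

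**Cost.** While enrolment is open: a short amendment, a computer-generated list, about 80 envelopes and a little time from one non-enrolling staff member, assuming one is available. No extra patients or procedures are needed. After enrolment, only labels, reporting and the wording of conclusions change.

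**Remaining limit.** The device is visible, so someone tracking past allocations could still guess about 68% of assignments with blocks of 4, 6 and 8, against 100% under strict alternation.

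### Do the mixed design labels and the loosely timed examination and blood-gas data require a change to the protocol?

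*Protocol*

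**What the plan says.** Section 3 of the protocol (Methodology) has separate entries for the type of design and the proposed design. The first reads "Cohort Study Design" and the second "Prospective Interventional Study". The sampling entry reads "Randomized sample". Under Study procedures the allocation is spelled out: "randomization will be done as follow: group A contains the patients with odd numbers and group B contains patients with even numbers".

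The inclusion criteria admit children "hospitalized in PICU with acute respiratory distress failed on low flow nasal oxygen and need non invasive respiratory support".

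Three numbered items under Study procedures bear on timing:

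- Item 2 covers general examination and "respiratory examination for any residual findings at the time of the study, and retrieving data of examination findings from the medical files".
- Item 3 collects "Results of Laboratory tests done for patients during and after hospital admission including CBC, blood gases", together with inflammatory markers, cultures and a viral panel.
- Item 4 sets "chest ultrasound at day 0 then daily assessment by lung ultrasound score".

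The aim in section 2 concerns the outcome and tolerability of the two devices and names chest ultrasound as the means of assessment.

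**The concern.** Two things look wrong together. First, a study that assigns the treatment is not a cohort study in the usual sense, and random sampling from a population is not the same as random allocation to groups. A reader who sees only the design entries could not tell whether devices are assigned or merely observed.

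Second, some of the collection wording suits a look back after the illness rather than a comparison during it. Item 2 looks for residual signs although children are enrolled while acutely ill, and item 3 spans the admission and the time after it. Neither item refers to the start of the device. Children reach enrolment after low-flow oxygen has failed, so a blood gas taken during the admission might precede the device, fall while it is in use, or follow it.

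A gas taken before the device describes baseline, and one taken on it describes response. If the two were mixed, a comparison of gas exchange or respiratory signs would be hard to interpret, and the choice of value could be made after the data had been seen. The Introduction cites a record-based comparison of the same two kinds of support that looked at respiratory rate and PaCO2, so a reader may expect similar comparisons here.

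**Working it through.** No arithmetic applies. The sample size of 80 comes with no effect size, standard deviation or power, and it does not bear on this question. The check is to set the entries side by side and ask what each one leaves undecided.

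1. **Design label against procedure.** The design entries give two labels that do not fit together. Study procedures say that odd-numbered patients form one group and even-numbered patients the other, and section 3 says which device each group receives. The assignment is therefore made by the study, which matches "Prospective Interventional Study" and not "Cohort Study Design". The operative text settles the matter. Whether odd and even numbering deserves to be called randomization is a separate question and is not argued here.

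2. **The sampling entry.** "Randomized sample" puts the word in the wrong place, since nothing in the protocol describes random selection from a population. Study procedures already apply randomization to allocation, so moving the word changes nothing that is done.

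3. **Is timing absent from items 2 and 3?** Item 2 places the examination within the study and adds findings from the files. Item 3 gives a window of two periods, the admission and the time after it. Both are loose. Neither refers to device start or says which value is baseline and which is on-device. Nothing elsewhere in the protocol fills this in, so this part of the concern is confirmed.

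4. **Does it follow that the values cannot be separated?** That would require results and file entries to lack a date or time, or device start to go unrecorded. The protocol says neither. It lists what is collected and does not describe the data form. The inference is not supported by the text.

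5. **How many phases does the window mix?** Item 3 names two periods. Splitting them into three (before, on and after the device) is an interpretation. The inclusion criterion does not say where or when low-flow oxygen failed, so gases from before the device falling inside the window are plausible but inferred.

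6. **What depends on these values?** The assessment named in the aim is chest ultrasound, scheduled at day 0 and then daily. Blood gases and examination findings are not named as endpoints, and no test, threshold or sample-size figure in the protocol rests on them. The respiratory rate and PaCO2 comparison in the Introduction belongs to an earlier study, not to this plan.

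7. **What would the obvious edits change?** One design label, moving one word, deleting the reference to residual findings, and adding date and time fields would leave the allocation, the tests performed and every stated result as they are.

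**The case for a change.** The best case for a change is that the timing of data collection belongs in a protocol, and that an analysis plan cannot restore a time that nobody recorded. Item 4 shows that the authors could set a schedule when they chose to. Without a rule, the value treated as baseline or as response could be selected after the results are known. The repair is cheap: a single label and a date and time for device start and for each result, with no extra test or visit. Recording device start would also help to anchor day 0 of the ultrasound, which the protocol does not define relative to the device.

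Much of this stands as a description. The labels do conflict, items 2 and 3 are loosely timed, and day 0 is not anchored to device start. It does not establish a fault that needs an amendment. The risk of lost times assumes a recording failure that the document does not describe. The scope for selecting values matters most for a named endpoint, and these are not named endpoints. Choosing which dated value serves as baseline is commonly left to the analysis plan, which is not shown here. Date and time fields alone would not settle that choice in any case.

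**Conclusion.** No change to the plan is called for. The design label and the sampling entry are clerical slips, because the Study procedures already fix what is done for all 80 children. The missing time points for examination and blood-gas values are a gap that a data form and an analyst would ordinarily fill, by using dated results and the recorded start of the device.

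No effect on the ultrasound score is shown, and no effect size for any other measure can be derived from the document. The conclusion rests on two assumptions: that laboratory results, file entries and device start carry dates and times, as is usual in an intensive care unit, and that blood gases and examination findings remain supporting data. If either proved false, comparisons of those values between devices would lose much of their meaning, but the scheduled ultrasound comparison would not be shown to be affected. Authors who revise the text for other reasons could reasonably use one interventional label and state how day 0 relates to device start. That would be tidying, not correction of a result.

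### Is the 0.005 significance threshold a slip for 0.05 that has to be corrected?

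*Protocol*

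**What the plan says.** The Statistical analysis item in section 3 (Methodology) has two parts. It first describes summaries: "Numerical data will be summarized using mean and standard deviations or medians and inter quartile ranges", with counts and percentages for qualitative data. It then sets the decision rule: "p-value <0.005 will be considered significant". No other significance level appears in the protocol, and neither sidedness nor multiplicity is mentioned.

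The sample size entry in the same section reads "80 patients will be divided into 2 groups". It gives no power, target difference, standard deviation or significance level. Allocation is by patient number: "group A contains the patients with odd numbers and group B contains patients with even numbers". That implies about 40 per group.

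The aim in section 2 has two parts: "To study outcome & tolerability of High Velocity Nasal Insufflation and Continuous Positive Air way Pressure", assessed by chest ultrasound. The ultrasound data come from "chest ultrasound at day 0 then daily assessment by lung ultrasound score".

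**The concern.** A reader expects 0.05 here. A value ten times smaller, placed without comment after a sentence on descriptive summaries, looks like an extra zero. A deliberate strict level would normally come with a reason. The value equals 0.05/10, a Bonferroni level for ten tests, but the protocol describes no family of ten tests.

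If it is a slip, the trial gives up power for no purpose. A difference between the two devices with a p-value between 0.005 and 0.05 would have to be called not significant, in a trial of only 80 children. The threshold decides what the trial may claim, so the question deserves a check.

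**Working it through.** **Is there a figure to reproduce?** No. The sample of 80 cannot be re-derived, because the protocol gives no power, effect size, SD or dropout. So no sample-size calculation exists that used a different level and would show 0.005 to be inconsistent. What can be worked out is the consequence of each level.

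**Inputs**
- From the protocol: total 80, two groups, threshold 0.005.
- Implied by odd/even numbering: n = 40 per group.
- Assumed: two-sided test, 80% power, no dropout, unadjusted comparison of two means. Differences are in SD units because no SD is given.

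**Detectable difference, normal approximation:** d = (z for alpha/2 + z for power) × √(2/n), with √(2/40) = 0.2236.
- At 0.05: (1.960 + 0.842) × 0.2236 = 0.626 SD.
- At 0.005: (2.807 + 0.842) × 0.2236 = 0.816 SD.
- Ratio 1.30.

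**The same with the noncentral t distribution, 78 degrees of freedom:** the critical values are 1.991 and 2.889.
- At 0.05: 0.634 SD.
- At 0.005: 0.837 SD.
- Ratio 0.837/0.634 = 1.32.

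**How far the ratio depends on the assumptions**
- 90% power: 0.734 and 0.938 SD (noncentral t), ratio 1.28.
- One-sided, 80% power: 0.556 and 0.764 SD (normal approximation), ratio 1.37.
- Adjusting for the day-0 value multiplies both differences by √(1 − r²). At an assumed correlation r of 0.5 they become 0.549 and 0.725 SD, and the ratio stays at 1.32.

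**Power, unadjusted, noncentral t**

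| True difference (SD) | at 0.05 | at 0.005 | loss (points) |
|---|---|---|---|
| 0.5 | 59.8% | 26.5% | 33.3 |
| 0.6 | 75.5% | 42.4% | 33.1 |
| 0.7 | 87.1% | 59.7% | 27.4 |
| 1.0 | 99.3% | 94.0% | 5.3 |

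The loss peaks at 33.9 points, at 0.547 SD.

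**Sample size to keep 80% power at the difference detectable at 0.05:** n is proportional to the square of the ratio. By the normal approximation, 40 × 1.302² = 67.8, so 68 per group.

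**What the strict level buys:** for k independent tests with no true differences, the chance of at least one false positive is 1 − (1 − alpha)^k. Ten tests is an assumption.
- At 0.05: 1 − 0.95^10 = 0.401.
- At 0.005: 1 − 0.995^10 = 0.049.

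So 0.005 costs power for moderate differences and little for large ones. If several outcomes are tested, it also holds the overall false-positive rate near 5%.

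**The case for a change.** The strongest case for a change is that this is not detail a protocol may leave to an analysis plan. The protocol itself fixes the threshold, and any analysis plan must either inherit it or contradict it. If it is a slip, up to a third of the power for moderate differences goes for nothing, and correcting it needs no extra patients or measurements.

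The figures stand, and so does the suspicion of a slip. It remains a suspicion, because the text supports neither reading over the other. Three further points weigh against a change.

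- The rule can be applied exactly as written; only its reason is unknown. A missing rationale, and a missing list of the comparisons it covers, are matters an analysis plan can supply. The protocol does not say that each laboratory result will be tested between groups, so the rule's reach is itself an inference.
- Moving to 0.05 is more than an edit. If several outcomes were tested at 0.05 without control, the protection shown above would be lost. Doing it properly means naming a primary outcome and a day, and settling how the rest are handled.
- Timing matters. The study period runs from December 2022 to December 2024, and odd/even numbering reveals the group. If anyone has already seen outcomes by group, loosening the threshold would be data-driven, and the stated rule would have to stay.

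**Conclusion.** The concern does not call for a change. The protocol sets one significance level, and nothing else in it conflicts with that level. There is no competing alpha, no stated power that the trial then misses, and no sample-size calculation built on 0.05. A strict level fixed in advance gives valid, conservative conclusions.

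Its price is a detectable difference of 0.84 SD instead of 0.63 SD. That rests on two-sided testing, 40 per group, 80% power and no baseline adjustment, all of which are assumptions. The ratio of 1.32 ranges from about 1.28 to 1.37 under the alternatives shown. For true differences of 1.0 SD or more, the loss is about 5 points or less.

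Whether that price was meant is a fair question for the sponsor, best asked before outcomes are examined by group. Until a slip is confirmed, the level is a trade-off between power and false positives. Estimates with 95% confidence intervals and exact p-values would let readers judge a result between 0.005 and 0.05 for themselves, and the present wording does not prevent reporting them.
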